### 2.1.3 Unmet medical need in BED

Patients with BED have significant functional impairment, decreased quality of life and psychiatric (primarily anxiety and mood disorders) as well as medical comorbidities, including obesity, type 2 diabetes and sleep problems [Kornstein 2017, Bellows 2015, Ling 2017].

While psychological and cognitive behavioral interventions have been recommended as first-line treatment [Hilbert 2017] and are supported by meta-analytic reviews, these treatments require specialized expertise and are often not widely available and/or costly. Furthermore, about 50% of patients with BED do not fully respond to psychological or behavioral treatments [Linardon 2018]. Currently available pharmacologic treatments, including those used off-label, are limited by unfavorable side effects. The CNS stimulant lisdexamfetamine (available in the US and Australia) is an amphetamine derivative with a significant abuse potential and is associated with cardiovascular adverse effects [Vyvanse® USPI].

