#### 9.2.8 Vital signs

Descriptive summary statistics by visit and study treatment will be provided for observed values and changes from baseline in pulse rate, respiratory rate, temperature, systolic and diastolic blood pressure, and body weight.

Notable blood pressure abnormalities will also be summarized descriptively.

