#### 9.4 Sample size

The sample size is based on the primary efficacy endpoint, change from baseline to Week 12 in the number of BE days per week.

In 2 studies using lisdexamfetamine in study participants with BED [McElroy 2016] the difference between lisdexamfetamine and placebo for this endpoint was -1.35 (SD = 1.6) and -1.66 (SD = 1.6) days per week. The corresponding effect size was 0.83 (95% CI: 0.60–1.05) and 0.97 (95% CI: 0.72–1.21), respectively. In the USA, lisdexamfetamine is categorized as a Schedule II medication. For this reason, a smaller effect size by ACT-539313 may still be considered clinically important if it has a better safety profile than lisdexamfetamine.

In an earlier study comparing topiramate to placebo in study participants with BED [McElroy 2007] the difference in the means of the changes from Baseline to Week 16 between topiramate and placebo was -1.0 with a common SD of 2.0, providing an effect size of 0.5 (95% CI: 0.3–0.7).

In a recent study with dasotraline, the LSmean reduction from Baseline in number of BE days per week was significantly greater for dasotraline vs placebo at Week 12 (-3.74 vs -2.75), for an effect size = 0.74 [McElroy 2020].

Based on the above, it is assumed that a treatment group difference of 1 BE day per week (corresponding to an effect size of 0.5 to 0.7, depending on the SD) is clinically meaningful.

The sample size is based on the power to detect a reduction of at least 1 BE day per week at Week 12 (with an SD of 1.6, this corresponds to an effect size of 0.65), between ACT-539313 and placebo, at a significance level of 5% two sided. Table 5 shows the sample size needed to detect a difference between placebo and ACT-539313 for different effect sizes.

	-	-		
Effect size	0.5	0.6	0.7	
Power				
90%	170	118	86	
80%	126	88	66	

Table 5Total sample size for 90% power

For a two-sided  $\alpha = 0.05$  and 1:1 randomization

The sample sizes reported in Table 5 are based on a t-test, but are also valid for a mixed model for repeated measures, retaining close to 90% (or 80%) power in the case of missing Week 11–12 data (up to 20%).

Table 6 shows the power to detect a difference between placebo and ACT-539313 for a sample size of 100–120 study participants.

Table 6Power for sample sizes of 100 and 120

Effect size	0.5	0.6	0.7
Sample size			
100	71%	85%	94%
120	78%	91%	97%

For a two-sided  $\alpha = 0.05$  and 1:1 randomization

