7.4 Electrocardiography

ECG analyses are based on data received from the central reader. Unless noted otherwise, ECG summaries and listings will include scheduled, re-test, and unscheduled assessments.

Descriptive summary statistics for each scheduled visit (re-test excluded) will be provided for observed values and change from baseline in ECG parameters (QT, QRS, QT corrected according to Fridericia's formula, QT corrected according to Bazett's formula, heart rate, and PR interval).

Marked ECG abnormalities are defined in Table 4. The number (%) of study participants with a marked ECG abnormality will be provided for each ECG parameter.

Percentages will be based on the number of participants having at least one post-baseline value for criteria based on post-baseline values only, or those having a baseline value and at least one post-baseline value per ECG parameter for criteria based on change from baseline. For non-mutually exclusive criteria (i.e., HR, PR and QRS), a subject will be counted only once in case of multiple occurrences but may be reported in more than one marked ECG abnormality criterion of a given parameter. For mutually exclusive criteria (i.e., QTc), only the subject's worst post-baseline value (or worst change from baseline value) will be counted.

ECG findings during the treatment period will be summarized separately and listed. ECG abnormality categories and findings will be sorted by descending frequency, first in the ACT-539313 treatment group and then in the placebo group. After this sorting, ECG

ACT-539313		Statistical Analysis Plan
ID-082A201		for Clinical Study Report
1 April 2022, page 35/60	Confidential	Version 3
		Doc No D-22,100

abnormality categories will be presented in alphabetical order with ECG finding sorted within ECG abnormality category in alphabetical order. All ECG values for study participants with at least one marked ECG abnormality during the treatment period will be listed.

ECG parameter	Criteria for marked ECG abnormalities	
QTcF, QTcB (ms)	$> 450 \text{ and} \le 480$	
	$> 480 \text{ and} \le 500$	
	> 500	
	$>$ 30 and \leq 60 increase from baseline	
	> 60 increase from baseline	
HR (bpm)	< 45	
	< 50	
	> 10 and ≤ 20 decrease from baseline	
	> 20 decrease from baseline	
PR (ms)	> 200	
QRS (ms)	> 110	

Table 4Marked abnormalities in ECG parameters

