7.5 Vital signs and body weight

Each summary will include only scheduled assessments (re-test excluded) and listings will include both scheduled and unscheduled assessments.

The change from baseline to each visit (Week 1, 2, 4, 6, 8, 10, 12) in vital signs (systolic and diastolic blood pressure, respiratory rate, temperature, body weight, and pulse rate) will be summarized. The observed values at baseline and each scheduled post-baseline visit will also be summarized.

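### The SAP drops the protocol's summary of notable blood-pressure abnormalities without declaring it, and its heart-rate criteria count only low values and decreases

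*SAP*

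**What the plan says.** **Blood pressure and pulse.** After the by-visit descriptive statistics for vital signs, protocol 9.2.8 adds: "Notable blood pressure abnormalities will also be summarized descriptively". SAP 7.5 plans the change from baseline at Weeks 1, 2, 4, 6, 8, 10 and 12, and then: "The observed values at baseline and each scheduled post-baseline visit will also be summarized". Its summaries use scheduled assessments only and exclude re-tests; its listings include unscheduled ones. It gives no threshold for blood pressure or pulse.

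**Declared changes.** SAP 12.1 declares one departure from the protocol, the analysis sets for demographics and disease characteristics. SAP 12.2 to 12.4 are marked not applicable. The SAP revision history does not mention a removed blood-pressure output.

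**ECG.** The footnote to protocol Table 2 leaves the choice of marked ECG abnormalities to the SAP. In SAP Table 4 the heart-rate criteria are below 45, below 50, a decrease of more than 10 and up to 20, and "> 20 decrease from baseline". QTc has high-value rows and increase rows, the largest being "> 60 increase from baseline". SAP 7.4 also says "Descriptive summary statistics for each scheduled visit (re-test excluded) will be provided for observed values and change from baseline in ECG parameters", heart rate included, and "ECG findings during the treatment period will be summarized separately and listed". It further lists all ECG values for participants with at least one marked abnormality in the treatment period.

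**The concern.** There are two gaps of different standing. The blood-pressure item is a discrepancy between documents: the protocol commits to an output, and the SAP neither delivers it nor says why. The heart-rate item contradicts nothing, because the protocol delegates those definitions, but it leaves one direction uncounted.

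Together they mean that the planned cardiovascular tables do not answer a basic safety question: how many participants in each arm had a notable rise at any time on treatment? Earlier human exposure was in healthy subjects for at most 10 days (protocol 2.4 and 4.4), whereas this trial treats patients for 12 weeks. If criteria are first written after unblinding, they can be suspected of having been chosen with the data in view.

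**Working it through.** The plan attaches no figure to this point, so the main check sets the provisions side by side.

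**1. Blood pressure.** The protocol has two elements: descriptive statistics by visit, and a summary of notable abnormalities. SAP 7.5 carries over the first. The second appears in neither SAP 7.5, the marked-abnormality tables (Table 4 is ECG, Tables 11 to 14 are laboratory) nor SAP section 12. It is missing and undeclared.

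**2. Heart rate.** Table 4 has four heart-rate rows: two low values and two decreases. High values: 0 of 4. Increases: 0 of 4. QTc has five rows: three high-value bands and two increases.

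**3. Remaining routes to a high-side value.**

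| Planned output | What it gives | What it does not give |
|---|---|---|
| By-visit summaries (SAP 7.4, 7.5, 9.1) | n, mean, SD, median, quartiles, minimum, maximum | Number of participants ever abnormal across visits |
| ECG findings (SAP 7.4) | Counts of central-reader findings, possibly a fast rhythm | Blood pressure or visit pulse; only one post-baseline ECG is scheduled (protocol 7.2.5.3) |
| TEAEs (SAP 7.2) | Counts by SOC and preferred term | Anything the investigator did not record as an AE |
| Vital-sign listings (SAP 7.5) | Every individual value | A count by arm |
| Marked-abnormality ECG listing (SAP 7.4) | All values for flagged participants | Participants whose only abnormality is a high rate |

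Laboratory data are treated differently. SAP 7.3 counts participants with marked abnormalities, using high and low limits for parameters such as potassium and glucose, and gives shifts to the worst value for selected parameters.

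**4. What the retained statistics can show.** The input from the documents is 60 per arm (protocol 9.4). The documents give no SD for changes in heart rate or blood pressure, so 8 to 12 units is assumed.

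- Mean shift: 95% half-width = 1.96 × SD × √(2/60). For SD 8, 10 and 12 this is 2.9, 3.6 and 4.3 units. The planned summaries do inform on a mean shift.
- Tail: a quarter of 60 is 15. A subgroup of 6 (10%) can lie wholly above Q3, so the quartiles barely register it. The maximum shows one value per visit and arm.
- Chance that there is anything to count: 1 − (1 − p)^60. For assumed true rates p of 2%, 5% and 10% this is 70%, 95% and 99.8%.

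**5. Background noise in a count.** For illustration only, take pulse, a rise above 20 (the size of Table 4's largest decrease row), no mean shift and normal changes. Per visit, P = 1 − Φ(20/SD), which is 0.6%, 2.3% and 4.8% for SD 8, 10 and 12. At any of seven visits, if these were independent, 1 − (1 − P)^7 is about 4%, 15% and 29%; positive correlation between visits lowers this. Chance outliers should therefore be expected in both arms, and the count has to be read against placebo.

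**The case against.** The strongest reply is that little is lost. The vital-sign endpoint in protocol Table 2 is change from baseline, which the SAP retains in full. SAP 9.1 includes the maximum, so a large individual rise would show. Individual vital-sign values are listed, SAP 7.1 says generally that safety data are listed, ECG findings and TEAEs are counted, and Phase 1 found no treatment-related effect on vital signs or ECG (protocol 4.4). The low-side heart-rate criteria breach nothing. Much of this stands: it makes the point modest and rules out any claim that the SAP reports only means or hides high values. It does not supply the summary the protocol promised, or a count over visits.

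A reader might also infer that the trial's accepted effect size depends on a cardiovascular advantage that these tables could not show. Protocol 9.4 says "a smaller effect size by ACT-539313 may still be considered clinically important if it has a better safety profile than lisdexamfetamine", and protocol 2.1.3 says that lisdexamfetamine "is associated with cardiovascular adverse effects". The documents do not support that reading. Protocol 9.4 gives Schedule II status as the reason and speaks of safety in general; the cardiovascular remark is background, beside abuse potential. The 1-day target also draws on the topiramate and dasotraline studies. There is no lisdexamfetamine arm (protocol 4.3), so no table in this trial could show an advantage over that drug directly.

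**Conclusion.** The point holds in a limited form. The missing blood-pressure summary is a real, undeclared departure from protocol 9.2.8. The one-sided heart-rate criteria are a gap in the SAP's own definitions, not a contradiction of the protocol. The consequence is that raised blood pressure and pulse over seven post-baseline visits, and raised heart rate at the scheduled post-baseline ECG, have no participant count in the vital-sign tables or Table 4. No estimate, test or power figure changes. The provisions can be read directly from the documents; only the SDs, outlier rates and independence between visits used for illustration are assumed, and the conclusion does not depend on them. It is worth correcting because it restores a planned safety output at small cost.

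**What to change.** Before unblinding:

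- In SAP 7.5, add the number and percentage of participants by arm with a notable blood-pressure abnormality at any post-baseline visit, and the same for pulse, using the sponsor's standard reporting definitions. State whether unscheduled and repeat measurements count.
- In Table 4, add high-value and increase-from-baseline rows for heart rate, so that such participants also enter the marked-abnormality ECG listing.
- If the sponsor prefers to leave out the blood-pressure summary, declare and justify that in SAP 12.1.

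The cost is SAP wording and a few descriptive rows from data already collected. The downside is that some chance outliers will appear in both arms, so the rows should be presented as a descriptive comparison with placebo.

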7.5 Vital signs and body weight

Each summary will include only scheduled assessments (re-test excluded) and listings will include both scheduled and unscheduled assessments.

The change from baseline to each visit (Week 1, 2, 4, 6, 8, 10, 12) in vital signs (systolic and diastolic blood pressure, respiratory rate, temperature, body weight, and pulse rate) will be summarized. The observed values at baseline and each scheduled post-baseline visit will also be summarized.

7.6 Daytime sleepiness

Daytime sleepiness will be assessed using the SSS during the first two weeks of study treatment. The SSS is filled in twice daily, at breakfast before morning dose (pre-dose) and around midday, prior to lunch time (post-dose).

The SSS is a 1-item, 7-point scale that ranges between "Feeling active, vital, alert, or wide awake" and "No longer fighting sleep, sleep onset soon; having dream-like thoughts".

Daytime sleepiness is defined daily as any score > 3 on the SSS after the morning dose (post-dose).

The number of days per week with daytime sleepiness is defined as the number of diary days with at least an SSS score > 3, during the first 2 weeks of treatment only, divided by

ACT-539313		Statistical Analysis Plan
ID-082A201		for Clinical Study Report
1 April 2022, page 36/60	Confidential	Version 3
		Doc No D-22,100

the total number of diary days, times 7. A minimum of 7 diary entries during this 14-day time interval is required, otherwise the number of daytime sleepiness days will be considered missing. A diary day is a day for which the rate of daytime sleepiness is entered in the study participant's diary. This approach uses implicit imputation: if a subject does not have 14 entries but has at least 7, missing data points are given the same value as the mean of the non-missing data points of that same time point or week.

The mean number of days with daytime sleepiness pre- and post-dose during the 2-week period will be summarized by treatment group. In addition, the observed value and change from baseline at each study day will be summarized by treatment group. The number (%) of study participants with a post-dose SSS score ≤ 3 , 4, 5, 6 and 7, having a pre-dose SSS score ≤ 3 and equal to 4 will be provided by treatment group.

The SSS score pre- and post-dose over the 2-week period will be produced by treatment group using series plot (mean \pm SE) and boxplots. In addition, the series plot will be provided only for study participants with AESIs.

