- 8. All participants will be asked to return for an EOT visit. For participants who prematurely discontinue study treatment, the EOT visit will occur within 5 days of the last intake of study treatment. For participants who complete the treatment period as planned, the Week 12 visit corresponds to the EOT visit.
- 9. During unscheduled visits, additional assessments may be performed at the discretion of the investigator. The assessments in brackets are recommended to be performed on an unscheduled visit, based on medical judgment.

10. Stanford Sleepiness Scale to be filled in for the first 2 weeks of study treatment, twice daily, at breakfast (before morning dose) and around midday, prior to lunch time.

AE = adverse event; BP = blood pressure; BWSQ = Benzodiazepine Withdrawal Symptom Questionnaire; CGI-C = Clinical Global Impression of Change scale; CGI-S = Clinical Global Impression of Severity scale; C-SSRS© = Columbia Suicide Severity Rating Scale©; eCRF = electronic Case Report Form; ECG = electrocardiogram; EDE-Q: Eating Disorder Examination Questionnaire; EOS = End-of-Study; EOT = End-of-Treatment; HAMD-17 = Hamilton Rating Scale for Depression (17-item); ICF = informed consent form; IMP = Investigational Medicinal Product; IRT = Interactive Response Technology; MINI© = Mini International Neuropsychiatric Interview©; NA = not applicable; PGI-C = Patient Global Impression of Change scale ; PGI-S = Patient Global Impression of Severity scale; PK = pharmacokinetic(s); PR = pulse rate; RR = respiratory rate; SAE = serious adverse event; SCID-5 = Structured Clinical Interview for DSM-5; To = temperature; U1 = unscheduled visit; V = visit; WOCBP = women of childbearing potential; YBOCS-BE = Yale-Brown Obsessive-Compulsive Scale Modified for Binge Eating.

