Dose-related somnolence was reported in the MAD study (4/28, 14.3%) and was not observed in subjects treated with placebo. The dose of ACT-539313 selected for this Phase 2 trial for treating BED in humans aims at an exposure resulting in selective antagonism of OX1R, avoiding sleep induction. Nonetheless, potential safety risks from daytime somnolence will be mitigated by excluding from study participation those individuals whose work requires them to operate heavy machinery [see Section 5.4]. In addition, excessive daytime sleepiness following study drug intake will be regularly assessed until the ability to remain alert while taking the drug is established. Cautionary advice will be given by the investigator with respect to activities requiring complete mental alertness, including driving. Standard monitoring and reporting of AEs, including assessment of prespecified AEs related to somnolence will be put in place [see Section 8].

Hematologic and hepatic variables were unaffected in the Phase 1 studies. Liver and hematology variables will be monitored in this study.

ACT-539313 is not teratogenic nor embryotoxic in rats and rabbits. However, not all reproductive toxicity studies of ACT-539313 have been performed at this stage; therefore, ACT-539313 may be given to WOCBP only when absence of pregnancy has been verified. WOCBP must use a highly effective method of contraception during treatment and for 1 month after end of study treatment [see Section 5.5].

More information about the known and expected benefits, risks, and anticipated AEs can be found in the IB [ACT-539313 IB].

It is the investigator's/delegate's responsibility to monitor the benefit/risk ratio of study treatment administration, as well as the degree of distress caused by study procedures on an individual study participant level, and to discontinue study treatment or the study if, on balance, he/she believes that continuation would be detrimental to the study participant's wellbeing. Provided the protocol is adhered to, exclusion criteria, careful observation, and medical management will minimize any associated risk in this study. Overall, the benefit/risk assessment supports the conduct of the proposed ID-082A201 study.

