# 9.2.10 Specific safety endpoints

*Daytime sleepiness* is defined daily as any score > 3 on the SSS after taking the morning dose. It will be collected on Days 1–14 and expressed as a number of days per week (as for the primary efficacy outcome). A minimum of 7 diary entries are required, otherwise the data will be considered missing. The mean number of days with daytime sleepiness per week will be summarized by treatment group.

The number (%) of study participants with *suicidal ideation and/or behavior* based on the C-SSRS© will be tabulated by visit and treatment group.

*Withdrawal effects* will be described summarizing changes from changes from Week 12/EOT to EOS in BWSQ and HAMD-17 by treatment group.

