For the calculation of SSS, study days falling in the time window 2-15 will be considered for the analyses since study day 1 corresponds to assessments done on the day of the randomization where information on the SSS should not be collected.

11.8 Time window definitions for calculating exploratory efficacy and safety endpoints collected during site visits

The exploratory efficacy endpoints YBOCS-BE, PGI-S, CGI-S, PGI-C, CGI-C, EDE-Q, and HAMD-17 are collected during specific site visits [Table 7].

The safety endpoint C-SSRS[©] is collected during all site visits [Table 8].

For both efficacy and safety endpoints, if more than one assessment falls within the same time window, the assessment which is performed closest to the target study day will be considered for the analysis.

Table 7Time windows (in days) for visit-based exploratory efficacy
endpoints: YBOCS-BE, PGI-S, CGI-S, PGI-C, CGI-C, EDE-Q,
HAMD-17

Week	Target study day	Window	Endpoint
Baseline	1	1–1	YBOCS-BE, PGI-S, CGI-S, EDE-Q, HAMD-17
1	8	2-14	CGI-C, PGI-C
4	29	22-36	YBOCS-BE, PGI-S, CGI-S, PGI-C, CGI-C, EDE-Q
6	43	37–49	HAMD-17
8	57	50–64	YBOCS-BE, PGI-S, CGI-S, PGI-C, CGI-C, EDE-Q
12	85	78–92	YBOCS-BE, PGI-S, CGI-S, PGI-C, CGI-C, EDE-Q, HAMD-

CGI-C = Clinical Global Impression of Change scale; CGI-S = Clinical Global Impression of Severity scale; EDE-Q = Eating Disorder Examination Questionnaire; HAMD-17 = Hamilton Rating Scale for Depression (17-item); PGI-C = Patient Global Impression of Change scale; PGI-S = Patient Global Impression of Severity scale; YBOCS-BE = Yale-Brown Obsessive-Compulsive Scale modified for Binge Eating.

Table 8Time windows (in days) for C-SSRS©

Week	Target study day	Window	
Baseline	1	1–1	
1	8	5-11	
2	15	12–18	
4	29	22–36	
6	43	37–49	
8	57	50–64	
10	71	65–77	
12	85 78–92		

C-SSRS[©] = Columbia-Suicide Severity Rating Scale[©]

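### The 7-entry minimum can remove participants who stop in the first week from the days-per-week sleepiness summary, and no other planned output cleanly counts who had a sleepy day

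*SAP*

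**What the plan says.** SAP 7.6 calls a day sleepy when the Stanford Sleepiness Scale (SSS) score after the morning dose exceeds 3. It divides sleepy days by diary days over the first two weeks of treatment and multiplies by 7. It then adds: "A minimum of 7 diary entries during this 14-day time interval is required, otherwise the number of daytime sleepiness days will be considered missing". Protocol 9.2.10 has the same rule, "A minimum of 7 diary entries are required, otherwise the data will be considered missing", and models the measure on the primary efficacy outcome. The implicit imputation for gaps in SAP 7.6 applies only "if a subject does not have 14 entries but has at least 7".

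The windows differ. Protocol 9.2.10: "It will be collected on Days 1–14 and expressed as a number of days per week". SAP 11.7: "For the calculation of SSS, study days falling in the time window 2-15 will be considered for the analyses", because Day 1 is the randomization day. SAP 12.1 does not list this among the changes from the protocol.

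The collection period is also worded in two ways. Footnote 10 to the protocol's schedule of activities says: "Stanford Sleepiness Scale to be filled in for the first 2 weeks of study treatment, twice daily". Protocol 7.2.5.5 counts the two weeks from randomization instead.

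On the harm itself, Protocol 2.4 says: "Dose-related somnolence was reported in the MAD study (4/28, 14.3%) and was not observed in subjects treated with placebo". Somnolence is the adverse event of special interest (AESI) in Protocol 8.1.6.

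**The concern.** A completeness rule suited to a 12-week efficacy diary has been applied to a safety measure that lasts two weeks. A participant who becomes sleepy and stops early gives few entries, gets a missing value and leaves the mean. Missingness can then depend on the outcome. If the effect is dose-related, more participants would be lost on active drug, and the arm mean would tend to be too low.

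The plan deals with early stopping elsewhere. For absence of binge-eating episodes, too few entries or early discontinuation gives the unfavourable outcome (Protocol 9.2.4, SAP 6.3 and 11.7). The primary endpoint has two missing-not-at-random analyses (SAP 6.1.6). The sleepiness summary has no rule for early stoppers, no sensitivity version and no report of how many were set to missing.

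At stake is a descriptive, untested summary of the drug's known dose-related effect, in a trial whose dose was chosen to avoid inducing sleep (Protocol 2.4).

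**Working it through.** **Inputs.** Minimum of 7 entries (SAP 7.6, Protocol 9.2.10). Windows of days 2–15 (SAP 11.7) and Days 1–14 (Protocol 9.2.10). End-of-treatment visit 1 to 5 days after the last intake (Protocol 5.9.1). About 60 per arm (120 randomized 1:1, Protocol 6.1.3). Phase 1 somnolence 4/28 (Protocol 2.4).

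**Plan's own figure.** 4/28 = 14.3%, as stated.

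**Unit of an entry.** SAP 7.6 treats 14 entries as a complete 14-day record, so an entry is one day and not one of the two daily ratings.

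**Most entries possible if entries end with treatment:**

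| Last morning dose | SAP days 2–15 | Protocol Days 1–14 |
|---|---|---|
| Day 3 | 2, missing | 3, missing |
| Day 6 | 5, missing | 6, missing |
| Day 7 | 6, missing | 7, kept |
| Day 8 | 7, kept if none missed | 8, kept |

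Protocol 6.1.6.3 has a newly dispensed bottle started in the evening. If the first dose is therefore on the evening of Day 1, the first rating after a morning dose falls on Day 2. A Day 7 stopper then has 6 such ratings under the protocol window too.

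**If the card is kept after stopping.** With a last dose on Day 3 and entries up to a visit 5 days later, days 2–8 give 7 entries, 5 of them off drug. Sleepiness on both on-drug days would give 2/7 × 7 = 2 days/week, against 2/2 × 7 = 7 on treatment.

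**Illustration (assumed figures; the documents give none).** Sixty active participants, of whom k stop too early and were sleepy at rate r days/week. The others average m.

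- Reported mean = m, because the k participants are excluded.
- Mean with everyone = ((60 − k)m + kr)/60.
- Understatement = k(r − m)/60.

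With m = 1.0:

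| k | r = 7 | r = 5 | Reported |
|---|---|---|---|
| 2 | 1.20 | 1.13 | 1.0 |
| 3 | 1.30 | 1.20 | 1.0 |
| 5 | 1.50 | 1.33 | 1.0 |

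With r = 7 and m from 2 down to 0.5, the understatement is 5/60 to 6.5/60 = 0.08 to 0.11 for k = 1. It is 15/60 to 19.5/60 = 0.25 to 0.325 for k = 3, and 30/60 to 39/60 = 0.50 to 0.65 for k = 6.

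**Pooled alternative.** Take k = 3, each sleepy on all of 6 entries, and 57 others with 14 entries and 2 sleepy days each (1.0 day/week). Sleepy days: 57 × 2 + 18 = 132. Entries: 57 × 14 + 18 = 816. Rate = 132/816 × 7 = 1.13 days/week. This lies between the planned 1.0 and the equal-weight 1.3, because short records count only for the days they cover.

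**The case against.** The strongest reply is that somnolence is recorded in several other places. SAP 7.6 summarizes SSS by study day, and tabulates participants by post-dose score category (≤ 3, 4, 5, 6, 7) with no stated 7-entry minimum. SAP 7.2 tabulates AESIs overall and by 2-week interval, and also adverse events leading to discontinuation. Investigators must ask about somnolence at every visit (Protocol 8.1.6). This stands. A reader might infer that the trial could report no excess sleepiness when there is one. The documents do not support that, because a cluster of first-week stoppers would show in these outputs.

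The outputs do not fill the gap exactly. By-day summaries lose a participant from the stop day onward. The category table covers only pre-dose scores up to 4 and does not say whether it is by day or by worst value. Adverse event tables do not use the SSS.

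Three other stronger readings also fail:

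- **Everyone who stops in week 1 is lost.** This needs the SAP window, or no rating after a morning dose on Day 1, and it needs entries to end with treatment.
- **Off-drug days freely dilute the rate.** SAP 7.6 restricts the count to the first two weeks of treatment and to scores after the morning dose. Only the looser wording in Protocol 7.2.5.5 and the lack of an explicit cut at last dose leave the question open.
- **The minimum should simply be removed.** One sleepy entry would then become 7 days/week with full weight, which brings its own distortion.

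Finally, the effect may be small. Phase 1 had no discontinuations for adverse events (Protocol 2.2), and its adverse events were transient and mild or moderate (Protocol 4.4).

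**Conclusion.** The concern holds for one summary, mean days per week with sleepiness. Under SAP days 2–15, a last morning dose on or before Day 7 with no later entries always gives a missing value. The loss can be related to the harm. The direction, too low in the active arm, rests on two assumptions: somnolence is dose-related here as in Phase 1, and some participants stop early because of it. The size cannot be taken from the documents. In the illustration above, 1 to 6 such participants among 60 shift the mean by about 0.1 to 0.65 days/week. With none, the shift is zero.

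This is a cheap improvement to safety reporting. It does not threaten the trial's ability to detect somnolence.

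**What to change.** In SAP 7.6, keep the 7-entry mean and add, by arm:

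- **(a)** Among Safety set participants with at least one post-dose entry, the number (%) with at least one on-treatment day with post-dose SSS > 3.
- **(b)** A sensitivity rate without the minimum, for example total sleepy days divided by total on-treatment days with a post-dose entry, times 7, so that one or two entries do not get full weight.
- **(c)** The number set to missing by the 7-entry rule, with the reason.

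Define an on-treatment day for this purpose from the treatment end date in SAP 11.1. State whether the score-category table is by day or by worst value.

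Reconcile the analysis windows (Protocol Days 1–14, SAP days 2–15) and list any change in SAP 12.1. Reconcile the collection wording in the schedule footnote and Protocol 7.2.5.5.

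The cost is SAP wording and a few table rows, from data already collected. The downside is that rates built on few entries are noisier, which is why (b) is offered as a sensitivity display beside the planned mean.
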